4 STUDY POPULATION

The study population will consist of adult female patients diagnosed with, or with a high clinical suspicion of, ovarian cancer who are scheduled to undergo primary surgical cytoreduction, interval debulking, or recurrent ovarian cancer surgery. For a full list of eligibility criteria, refer to Section 5.2 of the protocol.

5 TREATMENT ASSIGNMENT

The study design results in an open-label single-arm for the assessment of efficacy and safety. There is (are) no comparator group(s), and it is anticipated that all participating patients will receive OTL38. However, some patients receiving OTL38 will be randomized to undergo lesion assessment under normal light only and will not undergo fluorescent imaging. The goal of the randomization is not the assignment of patients to a comparator group, but to guard against the

possible “under-calling” of lesions during the normal light assessment by creating the possibility that any patient, following evaluation by normal light, may not continue to assessment by fluorescent imaging. To achieve this safeguard, a blinded randomization of patients to undergo fluorescent imaging, or not, will occur after normal light assessment, but prior to fluorescent imaging or surgery. The randomization will be generated from a single centralized randomization.

[REDACTED]

Patients receiving OTL38 and randomized to not to undergo fluorescent imaging will be evaluated for safety only.

6 SAMPLE SIZE DETERMINATION

[REDACTED]

[REDACTED]

[REDACTED]

[REDACTED]

[REDACTED]

7 GENERAL ANALYSIS AND REPORTING CONVENTIONS

The following is a list of general analysis and reporting conventions to be applied for this study.

- Baseline will be defined as the last recorded non-missing observation prior to exposure to study drug.
- Categorical variables will be summarized using counts (n) and percentages (%) and will be presented in the form “n (xx.x)”. Percentages will be based on the relevant total category count excluding missing data if not otherwise mentioned. To ensure completeness, where relevant, summaries for categorical and discrete variables will include all categories, even if no patients had a response in a particular category.
- Continuous variables will be summarized using mean, SD, minimum, maximum, median, and number of patients. The mean and median will be reported to one more level of precision than the original observations, and the SD will be reported to 2 more levels of precision than the original observations. The minimum and maximum will be the same precision as the original data.
- For tests of hypotheses, the associated p-value and confidence interval (CI) will be reported, where applicable. All p-values will be rounded to 3 decimal places; p-values that round to “0.000” will be presented as “<0.001”.
- Dates will be displayed as ddmmmyyyy (e.g., 24Jan2005).
- Age (in years) will be calculated using the date of birth and the date of informed consent as (date of informed consent – date of birth) / 365.25.

8 ANALYSIS POPULATIONS

The following definitions will be used to derive the analysis sets for the study.

8.1 Full Analysis Set (FAS)

The FAS for the primary analysis of the primary endpoint will include patients exposed to OTL38 and randomized to undergo fluorescent imaging (OTL38+Imaging) who:

- Were evaluated under both normal light and fluorescent light imaging, and
- Had central pathology and histology confirmation for at least one FR+ Ovarian Cancer lesion detected under normal light or fluorescent light imaging

For the evaluation of the primary efficacy endpoint, only the evaluable lesions contributed by FAS subjects will be considered (see Section 8.4). The FAS will also be referred to as the modified Intent-to-Treat (mITT) analysis set.

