3.4 Risks and Benefits of OTL38

3.4.1 Risks

The issues of possible concerns with the use of the OTL38 imaging systems are:

- Presence of an imaging system in the operating room
- Phototoxicity or thermal damage from the light source
- Nonspecific localization of OTL38
- Failure of OTL38 to bind to receptors
- Fading of the chromophore (photobleaching)
- Inability to excite the dye in OTL38 or to record emission
- Adverse events suggestive of hypersensitivity

[Redacted text block]

[Redacted text block]

[Redacted text block]

[Redacted text block]

[Redacted text block]

[Redacted text block]

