8.2.2 Analysis Sets

The following definitions will be used to derive the analysis sets for the study.

Full Analysis Set (FAS): The FAS for the primary analysis of the primary endpoint will include subjects exposed to OTL38 and randomized to undergo fluorescent imaging (OTL38+Imaging) who:

- Were evaluated under both normal light and fluorescent light imaging, and
- Had [REDACTED] pathology and histology confirmation (positive for FR+ Ovarian Cancer) for at least one lesion detected under normal light or fluorescent light imaging

[REDACTED]

Per Protocol Analysis Set (PPAS): The per protocol analysis set will include all patients meeting the FAS criteria in addition the following criteria:

- Meeting all the inclusion and none of the exclusion criteria
- Having no major protocol deviations

[REDACTED]

Safety Analysis Set (SAS): The safety analysis set will include all patients exposed to OTL38.

[REDACTED]

[REDACTED]

[REDACTED]

[REDACTED]

[REDACTED]

Pharmacokinetic Analysis Set: Every patient receiving a full dose of OTL038 and with one or more measurable drug-plasma concentrations will be included in the PK Analysis Set.

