8.3 Handling of Missing Data, Subject Withdrawals, and Treatment Failures

For the primary efficacy endpoint, all subjects included in the FAS will be included in the primary analysis.

For secondary and exploratory efficacy endpoints, patient inclusion for the analysis of a specific endpoint will depend on the lesion type or patient subgroup under specific consideration.

In general, missing safety data will not be imputed with the possible exception of missing or partial dates. Details will be included in the SAP.

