13.1.2 Sensitivity Analyses for the Primary Efficacy Endpoint

Sensitivity analyses for the primary efficacy endpoint will be conducted separately for the Per-Protocol analysis set. The analytic methods will follow those outlined for the primary analysis and include only evaluable lesions.

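### Patients randomised to fluorescent imaging but not evaluated under it leave the FAS/mITT, and no readable efficacy analysis of detection counts them, so failures that prevent imaging cannot lower the reported rate

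*SAP*

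**What the plan says.** SAP 8.1 starts the FAS from "patients exposed to OTL38 and randomized to undergo fluorescent imaging (OTL38+Imaging) who" meet two further conditions. The first is that they "Were evaluated under both normal light and fluorescent light imaging". The second is central confirmation of at least one FR+ ovarian cancer lesion found under either light. The section adds: "The FAS will also be referred to as the modified Intent-to-Treat (mITT) analysis set". Protocol 8.2.2 states the first condition in the same words: "Were evaluated under both normal light and fluorescent light imaging, and".

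On timing, SAP 5 says that randomisation "will occur after normal light assessment, but prior to fluorescent imaging or surgery".

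On robustness, SAP 13.1.2 says: "Sensitivity analyses for the primary efficacy endpoint will be conducted separately for the Per-Protocol analysis set". SAP 8.2 defines that set as FAS members who meet further criteria.

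On missing data, protocol 8.3, whose heading mentions treatment failures, says: "For the primary efficacy endpoint, all subjects included in the FAS will be included in the primary analysis". SAP 13.4 likewise speaks only of FAS members. SAP 13 also starts the secondary and exploratory efficacy analyses from the FAS.

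Among the issues of possible concern in protocol 3.4.1 is "Inability to excite the dye in OTL38 or to record emission".

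**The concern.** The product under test is a drug used with an imaging system. The first FAS condition depends on something that happens after randomisation, namely whether fluorescent evaluation took place. If it did not, the patient drops out of numerator and denominator together, although the set carries a modified intent-to-treat label.

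The primary endpoint is the proportion of patients with at least one additional confirmed lesion found by fluorescence alone. A patient never evaluated under fluorescence cannot have one, so the direction of any bias is known: zero or upward.

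The study is open-label and randomisation follows the normal-light record. If imaging were ever omitted by decision, that decision could depend on what had been seen. A surgeon considering the product would want the rate among patients in whom imaging was intended, and the readable plan specifies no such estimate.

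**Working it through.** **Step 1. Follow a patient who is dosed, randomised to imaging and not imaged.**

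| Analysis | Source | Is she counted? |
|---|---|---|
| Primary (FAS) | SAP 8.1, 13; protocol 8.2.2 | No |
| Sensitivity (per-protocol) | SAP 8.2, 13.1.2 | No, nested in the FAS |
| Missing-data rule, primary endpoint | SAP 13.4; protocol 8.3 | No, FAS members only |
| Secondary and exploratory detection | SAP 13 | No, these start from the FAS |
| Adverse device effects | SAP 14.3 | No, the denominator is imaged patients |
| Safety | SAP 8.3 | Yes |
| Disposition | SAP 9.1 | Yes, by randomised group, with no line for non-imaging |
| Demographics | SAP 10 | Yes, by randomised group |

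Disposition would not identify her, because she can still complete the study.

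**Step 2. Direction.** Let x be the successes among n FAS patients. Let k be the patients randomised to imaging but not evaluated under it who have a confirmed FR+ lesion detected under normal light. The plan reports x/n. Counting the k as non-successes gives x/(n+k) = (x/n) × n/(n+k), which never exceeds x/n.

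**Step 3. Size, for illustration.** The documents' only usable input is the minimum of 100 evaluable patients (protocol synopsis). I take this as n = 100 and take the whole FAS as the denominator, as protocol 8.3 does. SAP 13.4 adds a requirement of at least one evaluable lesion, which is a separate matter. The figure of 100 cannot be reproduced, because the null proportion, expected proportion and power are redacted. Both k and the 30% rate below are assumptions.

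| k | Factor 100/(100+k) | Rate if 30/100 in the FAS | Exact 95% CI |
|---|---|---|---|
| 0 | 1.000 | 30.0% | 21.2 to 40.0 |
| 2 | 0.980 | 30/102 = 29.4% | 20.8 to 39.3 |
| 5 | 0.952 | 30/105 = 28.6% | 20.2 to 38.2 |
| 10 | 0.909 | 30/110 = 27.3% | 19.2 to 36.6 |

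Under the written plan every row is reported as 30.0%.

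**Step 4. Could the test result change?** Only near the boundary. I take the two-tailed 0.05 exact test as an upper tail of at most 0.025.

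| Assumed null | Critical count at n = 100 | Smallest k at which that count is no longer significant |
|---|---|---|
| 5% | 11 | 13 |
| 10% | 17 (tail 0.0206) | 3 |
| 15% | 23 | 2 |
| 20% | 29 | 2 |

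With a null of 10%, 18 successes lose significance at k = 10 and 22 only at k = 42. The true null is not readable, so this is a range and not a finding about this trial.

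**The case against.** The strongest defence is that the plan openly limits efficacy to patients who had both assessments (protocol 5.1, SAP 3). Randomisation exists to deter under-calling under normal light, not to create a comparator (SAP 5), so no randomised comparison is broken. Performance when imaging is done is a legitimate target. That stands, and it is a reason to leave the primary set alone. It does not explain why the exclusions go without a dedicated count or a sensitivity estimate.

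Second, k may well be small. The window between randomisation and imaging is short, and at k = 5 the shift is 1.4 percentage points against a confidence interval nearly 19 points wide. This also stands, and it limits the point to a cheap improvement.

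Third, some of the information is recoverable. The number randomised to imaging (SAP 9.1) less the denominator for device effects (SAP 14.3) gives the number not imaged, crossovers aside. Deviations, imaging times and pathology are listed (SAP 9.2, 14.2, 14.7, 14.8). So a reader should not infer that the data could never yield an intended-to-image rate. What is missing is a pre-specified estimate and a table of reasons.

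Fourth, there are redactions. The intra-operative procedures (protocol 5.7.1.2.1), the text after the protocol's FAS definition and sensitivity sentence, and part of SAP 13.1 are blacked out, and a rule could sit there. SAP 8.1 and 13.1.2 show no gaps, but the claim has to be confined to readable text.

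**Conclusion.** The point holds for patients who were randomised to imaging and never evaluated under it. Their exclusion can leave the reported detection rate unchanged or raise it, never lower it, relative to the rate among FAS patients plus those excluded for this reason alone. The relative reduction on restoring them is k/(100+k) with 100 FAS patients: 4.8% at k = 5 and 9.1% at k = 10. The actual k is unknown and probably small.

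A reader might go further and infer that no failure of the technology can count against it, or that an unreliable camera would look as good as a reliable one. The documents do not support that. The FAS admits a patient through a confirmed lesion seen under either light. If she is imaged and nothing additional appears, she stays in through her normal-light lesion and lowers the rate. Only failures that prevent fluorescent evaluation escape. The risk listed in protocol 3.4.1 does not by itself mean that no evaluation took place, and the readable text names no specific cause of non-imaging, whether camera failure, aborted surgery or a surgeon's choice.

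**What to change.** Keep the primary FAS analysis unchanged.

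- **SAP 13.1.2:** add a sensitivity analysis with the same exact method. Its set is the FAS plus every patient exposed to OTL38 and randomised to imaging who was not evaluated under fluorescent light but has a centrally confirmed FR+ ovarian cancer lesion detected under normal light. Count the added patients as non-successes. Keeping the normal-light lesion requirement leaves the pathology condition of SAP 8.1 as it is, so 100/(100+k) describes the new analysis exactly when the FAS is 100.
- **SAP 9.1:** tabulate the number randomised to imaging but not imaged, by reason. Include those with no tissue excised, who cannot enter the sensitivity analysis because nothing can be confirmed. The readable text does not say whether imaging begun but not completed counts as evaluated, so state this in one line.

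The cost is some SAP wording, one table and a reason field on the eCRF. The sensitivity estimate may be slightly less favourable than the primary one. If nobody was missed, the two coincide and the table shows it.

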------------------------------------	--

Number of Subjects
	
A minimum sample size of 100 evaluable patients is required to evaluate the primary efficacy endpoint. [REDACTED]

Number of Investigator Sites
	
Up to 16 investigational sites (14 in the United States and 2 ex-U.S. [the Netherlands]).

Assessments
	
At specified time points as outlined in the schedule of events, patients will undergo the following procedures: collection of informed consent, medical history, demographics, physical exam including weight, vital signs including temperature, and ECG. Patients will also provide samples for clinical chemistry, CBC with differential, and a serum/urine test for women of child-bearing potential. Concomitant medications and adverse events as reported by the patient will be monitored.
 
Blood samples for PK analysis will be drawn from all subjects at sparse time points (30, 60 and 90 minutes) following the start of OTL38 infusion (see Section 6.5).
 
[REDACTED]

Study Endpoints
	
Primary Efficacy:
 
 Proportion of patients with at least one evaluable FR+ ovarian cancer lesion confirmed by [REDACTED] that was detected using the combination of OTL38 and fluorescent light but not under normal light or palpation. [REDACTED] 
[REDACTED]

	
Secondary Efficacy:
 
• False Positive Rate at the patient level (FPRp) [REDACTED]• Sensitivity or True Positive Rate (TPR) for OTL38 in combination with fluorescent light. [REDACTED]• False positive rate (FPR) for OTL38 in combination with fluorescent light, for the purpose of this protocol. [REDACTED] 
[REDACTED]
 
[REDACTED]
 

[REDACTED]	[REDACTED]	[REDACTED]	

[REDACTED]	[REDACTED]	[REDACTED]	

 
[REDACTED]
	[REDACTED]	[REDACTED]	[REDACTED]	[REDACTED]	[REDACTED]	[REDACTED]
[REDACTED]	[REDACTED]	[REDACTED]					
[REDACTED]	[REDACTED]	[REDACTED]					
	
[REDACTED]
 
[REDACTED]
 
[REDACTED]
 
[REDACTED]
						

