8.2 Per Protocol Analysis Set (PPAS)

The per protocol analysis set will include all patients meeting the FAS criteria in addition to the following criteria:

- Meeting all the inclusion and none of the exclusion criteria
- Having no major protocol deviations

- [REDACTED]
- [REDACTED]

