13.1 Analytic Methods for the Primary Efficacy Endpoint

The primary analysis of the primary efficacy endpoint will be a one-sample test for a proportion via an exact binomial test conducted at the two-tailed alpha level of 0.05. [REDACTED]

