13.2 Analytic Methods for Secondary Efficacy Endpoints

The patient level False Positive Rate (FPR_p) will be analyzed descriptively, providing the point estimate and the two-sided 95% Wilson (score) confidence interval. The analysis will be conducted using the FAS.

[REDACTED]

[REDACTED]

[REDACTED]

[REDACTED]

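### The FAS rule can remove only non-successes, so the primary rate is at or above the rate in all imaged patients, and no visible analysis shows by how much

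*SAP*

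**What the plan says.** SAP 8.1 builds the FAS from patients who were dosed, randomised to imaging and assessed under both lights, and who "Had central pathology and histology confirmation for at least one FR+ Ovarian Cancer lesion detected under normal light or fluorescent light imaging". Protocol 8.2.2 has the same rule: "pathology and histology confirmation (positive for FR+ Ovarian Cancer) for at least one lesion detected under normal light or fluorescent light imaging". Either method may supply the qualifying lesion.

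A primary-endpoint success (SAP 12.1) is a patient with at least one evaluable, pathology-confirmed FR+ ovarian cancer lesion found by fluorescence and missed by normal light and palpation. The test is a "one-sample test for a proportion via an exact binomial test conducted at the two-tailed alpha level of 0.05".

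On sensitivity analyses, SAP 13.1.2 says "Sensitivity analyses for the primary efficacy endpoint will be conducted separately for the Per-Protocol analysis set". SAP 8.2 defines that set: "The per protocol analysis set will include all patients meeting the FAS criteria in addition to the following criteria". For the patient-level false positive rate (FPRp), SAP 13.2 states "The analysis will be conducted using the FAS".

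The documents differ on who is counted. Protocol 8.3 puts every FAS subject in the primary analysis. SAP 13.4 counts only FAS patients who have at least one evaluable lesion.

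The primary objective (Protocol 4.1, SAP 2.1) is stated for patients with FR+ ovarian cancer. Enrolment (Protocol 5.2.1, SAP 4) also takes patients in whom ovarian cancer is only strongly suspected.

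**The concern.** Membership of the denominator is settled after surgery and depends partly on what the test under study found. A patient with a confirmed FR+ lesion seen under normal light enters whatever fluorescence shows. A patient without one can enter only through a fluorescence finding, and if that lesion is evaluable and was also missed by palpation she is a success. If fluorescence finds nothing confirmable in her, she leaves the denominator and is not counted as a failure.

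FR status and final histology are generally not established when the surgeon decides to image. The rate that applies at that moment is the one among all imaged patients, and the FAS rate can only equal or exceed it. Nothing in the visible plan lets a reader see the gap with a confidence interval, or learn why imaged patients were left out. FPRp has the same gap: an imaged patient whose fluorescent-only findings were all histologically negative, and who had no other confirmed FR+ lesion, is not counted.

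**Working it through.** **Inputs from the documents.** Exact binomial test, two-sided 0.05, taken here as 0.025 in the upper tail (SAP 13.1). Sample size: "A minimum sample size of 100 evaluable patients is required to evaluate the primary efficacy endpoint" (Protocol synopsis). The null rate, alternative rate and power are redacted in Protocol 8.2.1 and SAP 6, so the figure of 100 can be neither reproduced nor contradicted. The null rate p0, the dropped share d and the success counts below are assumptions for illustration.

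**Step 1: direction.** A success was imaged under both lights and has a confirmed FR+ lesion. Taking the partly redacted pathology standard in SAP 12.1 to be the central read of SAP 8.1, she always meets the FAS rule. Everyone the rule drops is therefore a non-success. With x successes, n patients in the FAS and k imaged patients dropped:

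- FAS rate = x/n
- all-imaged rate = x/(n+k)
- ratio = (n+k)/n = 1/(1-d), with d = k/(n+k)

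**Step 2: size against all imaged patients.** An all-imaged rate of 20% becomes 0.20/0.90 = 22.2%, 0.20/0.80 = 25.0% or 0.20/0.70 = 28.6% in the FAS at d = 10%, 20% or 30%. In counts, with an assumed 30 successes among 100 FAS patients:

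| Imaged patients restored (k) | Rate | Exact 95% CI |
|---|---|---|
| 0 | 30/100 = 30.0% | 21.2 to 40.0 |
| 5 | 30/105 = 28.6% | 20.2 to 38.2 |
| 10 | 30/110 = 27.3% | 19.2 to 36.6 |
| 20 | 30/120 = 25.0% | 17.5 to 33.7 |
| 30 | 30/130 = 23.1% | 16.1 to 31.3 |

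**Step 3: consequence for the test, conditional on a threshold set for all imaged patients.** Suppose the all-imaged rate equals p0, so that the FAS rate is p0/(1-d), with 100 patients in the FAS. Upper-tail rejection probability:

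| p0 | Critical count | d = 0 | 5% | 10% | 20% | 30% |
|---|---|---|---|---|---|---|
| 10% | 17 | 0.021 | 0.032 | 0.049 | 0.116 | 0.257 |
| 20% | 29 | 0.020 | 0.037 | 0.069 | 0.208 | 0.500 |

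Robustness depends on the margin. At p0 = 10%, a result of 17/100 loses significance once 3 imaged non-successes are restored; 22/100 loses it only at 42. At p0 = 20%, 29/100 is lost at 2 and 34/100 at 23.

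**Step 4: size against FR+ patients.** The same formula applies, but d now counts only imaged patients who truly have FR+ disease and were left unconfirmed. The documents give no figure for this share, so no size can be stated.

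**Step 5: the two denominators.** A success has an evaluable lesion by definition, so the SAP 13.4 restriction also removes only non-successes. With 30 successes and 100 FAS patients, if 5, 10 or 20 have no evaluable lesion, the Protocol 8.3 rate is 30.0% and the SAP 13.4 rate is 30/95 = 31.6%, 30/90 = 33.3% or 30/80 = 37.5%.

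**Step 6: FPRp.** Restoring patients changes numerator and denominator together. Assume 20/100 in the FAS and 20 patients restored. If 2 of them are false-positive-only, FPRp is 22/120 = 18.3%, which is lower; if 6 are, it is 26/120 = 21.7%, which is higher. The direction cannot be fixed in advance.

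**The case against.** The strongest reply is that the FAS rule is how the plan identifies its own target. The primary objective and FPRp are both defined for patients with FR+ ovarian cancer, a status that only pathology of removed tissue settles for many patients, and known FR-negative cancer is an exclusion criterion (Protocol 5.2.2). Leaving out benign disease and FR-negative cancer is then correct. This stands. A reader might infer that the primary rate is simply biased upward; the documents support that only against all imaged patients, plus an unsized contribution from truly FR+ patients left unconfirmed.

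A reader might also take the rejection probabilities in the working as the trial's error rate. They are not. The threshold is redacted, and if it was set for FR+ patients, dropping patients without FR+ disease leaves the size at its nominal value. The only visible anchor for d is Protocol 3.2, which puts FR expression in epithelial ovarian cancer above 90%. That suggests at most about 10% lost through FR-negativity; 20% and 30% have no source.

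A third tempting inference is that FPRp is understated. Step 6 shows that this is not established.

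Finally, Protocol 8.2.2, Protocol 8.2.5.2 and SAP 13.2 carry redactions and SAP 12.3 is wholly redacted, so an absence of other analyses can be asserted only for the visible text. SAP 13.1.2 itself shows no redaction. The exploratory proportions in SAP 13.3.2 adapt the FAS for other lesion types, not for the primary endpoint. Disposition (SAP 9.1) gives the number randomised to each group, so a crude rate can be worked out, but without a pre-specified interval or reasons for exclusion.

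**Conclusion.** The concern holds in limited form. By the definitions alone, the FAS rate is at or above the all-imaged rate by a factor 1/(1-d), and the visible sensitivity analysis cannot reveal the gap because its set lies inside the FAS. The size is unknown: for an assumed 30/100, the rate falls to 27.3% with 10 imaged patients restored and to 25.0% with 20. Against the stated FR+ target, the only upward bias comes from truly FR+ patients missed by both methods or without central confirmation, and it cannot be sized from the documents. The conflict between SAP 13.4 and Protocol 8.3 is separate, visible, and pushes the rate the same way. None of this invalidates the FAS as the primary set for the FR+ objective. The plan should be amended so that the dependence on the denominator can be seen.

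**What to change.** 1. Keep the FAS as primary for the FR+ objective. Reconcile SAP 13.4 with Protocol 8.3 so that one denominator is stated in both.
2. In SAP 13.1.2, add a pre-specified sensitivity analysis of the primary endpoint in all patients dosed, randomised to fluorescent imaging and imaged. Count anyone without a confirmed evaluable FR+ fluorescent-only lesion as a non-success, and give the exact 95% CI beside the FAS result.
3. Report the number of imaged patients excluded from the FAS and the reason for each, separating at least no cancer, FR-negative cancer and no central confirmation.
4. In SAP 13.2, add a supportive FPRp over all imaged patients, with the same numerator rule as the planned FPRp and no direction claimed in advance.
5. If rejection probabilities are quoted, state that they depend on an assumed d and on an assumed threshold set for all imaged patients.

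The cost is SAP wording, alignment of one protocol sentence if that is the text changed, and a few table rows from data already collected. The downside for the sponsor is a supporting figure for the primary endpoint that can only equal or fall below the FAS rate.
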